4 STUDY OBJECTIVES AND PURPOSE

This study will provide preliminary data on the safety of IDA treatment in persons with onchocerciasis when it is administered after pre-treatment with IVM to clear or greatly reduce microfilariae from the skin and eyes. Widespread use of IDA following IVM pretreatment (I/IDA) has the potential to greatly accelerate elimination of LF in African countries that are coendemic for LF and onchocerciasis.

Note that the sample sizes per treatment group in this study are not sufficient to conclusively demonstrate that IDA after IVM pretreatment is safe enough for widespread use in communities. Therefore, the safety study should be considered to be exploratory, and larger studies would be needed to formally establish safety of a pretreat/treat strategy with ivermectin followed by IDA (“I/IDA”). Having said that, a small exploratory safety study like this is an appropriate first step, because it should generate sufficient data to justify (or rule out) performance of a larger safety study later.

This study will also assess the efficacy of IDA for killing and sterilizing adult filarial worms. An improved macrofilaricidal treatment would be a major advance for the global program to eliminate onchocerciasis. Since the safety and efficacy objectives are both very important, we have included dual primary objectives for the study.

Primary Objectives:	
Safety: To compare rates and types of severe adverse events (grade 3 or higher) that occur within 7 days following 1 day or 3 days of treatment with triple drug treatment (“IDA” = DEC with ivermectin and albendazole) with the comparator regimen of 1 day of treatment with ivermectin and albendazole (IA) in persons with active Onchocerca volvulus infections after pretreatment with ivermectin alone.
 
Efficacy: To compare the effect of three treatment regimens (1 day of IDA, 3 days of IDA, or IA) for killing or sterilizing adult female O. volvulus worms based on the percentage of all adult female worms in nodules that are alive with embryos in the uterus 18 months after treatment.

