8 STATISTICAL CONSIDERATIONS

8.1 Sample Size Determination (Power calculation)

The *primary outcome* variable used for our power analysis is the % fertile female worms (100 x fertile female worms/ total female worms) for each of the three drug treatments: (1) single-dose IVM (IVM alone); (2) single dose of IVM + DEC and albendazole (IDA1); (3) three daily doses of IVM + DEC and albendazole (IDA3). Power calculations for our primary treatment-group comparison (IVM /ALB vs IDA1) assumed that 30% of the total worms will be fertile females in IVM/ALB group and that 15% of the total worms will be fertile females in the IDA1 group. For our secondary treatment-group comparison (IVM/ALB vs IDA3), we assumed that 10% of the total worms were fertile females for the IDA3 group. On average, we assumed that there will be 6 total female worms to evaluate in 3 nodules per person after treatment. In our analysis we treated each worm within a subject as a Bernoulli trial (0=non-fertile female worm, 1=fertile female worm), and we used an intra-class correlation (ICC) of 30% to account for within subject correlation among the trials. The ICC and cluster size (# female worms/person) adjusts the sample-size estimate using the following formula: $1 + \text{ICC} \times (\text{Cluster size} - 1)$ ^{44, 45}. To achieve 80% power at a two-sided alpha-level of 0.05, we will need nodule histology data from 51 subjects in each treatment group for the primary treatment-group comparison (IVM/ALB vs IDA1). The expected % difference for our secondary treatment-group comparison (IVM/ALB vs IDA3) powered at 80% and an alpha of 0.05, would require 26 subjects/group. After accounting for a 20% drop-out rate, a sample size of at least 61 subjects per treatment group will enable us to address both the primary (IVM/ALB vs IDA1) and secondary (IVM/ALB vs IDA3) treatment-group comparisons. Furthermore, we will attempt to enroll additional subjects beyond the target of 61 to provide some protection against other (unforeseen) factors that could decrease the power of this study (e.g., within village correlation, smaller effect size, higher drop-out rate than anticipated). The study will provide preliminary safety data, but a much larger study will be required to provide a precise safety comparison of IVM/ALB vs IDA.

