8.2 Data Analysis Plan

Efficacy analysis for primary outcome

Because of the within subject correlation for the primary outcome (% fertile female worms), we will use a generalized linear mixed model approach (PROC GLIMMIX, SAS)⁴⁶. Generalized linear mixed models (GLMM) permit modeling of non-normal outcomes while accounting for correlation among observations within a group. In the present study, the primary outcome is binary (0=non-fertile female worm, 1=fertile female worm) and worms within a person are not independent. To model these data we will use a GLMM assuming a binomial distribution with a logit link function,

and person will be treated as a random effect. Further, while we do not anticipate an effect of village on our outcomes, if subjects within village are correlated the GLMM can be extended to account for this correlation. A two-sided P -value ≤ 0.05 is considered significant for these analyses.

Efficacy analysis for secondary outcomes

Similar to the analysis of the primary outcome, percentage of all adult worms that are viable will be analyzed using a GLMM. Percent of persons with zero MF at 18 months will be analyzed using a generalized linear model assuming a binomial distribution and a logit link function. The difference between pre and post treatment MF counts (% reduction) will be analyzed using a paired t-test and will be transformed as necessary to meet the assumptions of this analysis. A P -value of 0.05 will be considered significant for all secondary outcomes.

Safety

The primary safety analysis will focus on AEs with severity grade 3 or greater. Secondary analyses will separately consider all AEs and ocular AEs. AEs will be assessed daily for 7 days after treatment and 3 months after treatment. This will include general assessments and detailed ophthalmological examinations on day 7 and 3 months after treatment. AE rates and severity will be compared across the three treatment groups using logistic regression analysis; with Student's t -test will be used to assess differences for individual AEs. The data will also be examined using a generalized linear mixed model that as described below can model non-normal outcomes and examine correlations among the different events and how these change over time. In this model, we can also examine the impact of baseline Mf burdens prior to treatment and other potential risk factors (age, sex, location, etc.) on AEs.

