Note that the samples sizes per treatment group in this study are not sufficient to provide a robust safety profile (e.g., high confidence that the rate of SAEs after treatment is less than 0.1%). This proof of concept study will allow for initial safety assessments to be performed. Additional, larger studies will be required to establish a more complete safety profile. The safety assessments put in place for this study along with the frequent and ongoing review by the DSMB will provide a strong foundation to evaluate the participant's safety throughout the study.

Data from all participants in this study will be analyzed for safety and efficacy outcomes. The study population for the primary and secondary endpoints related to adult worm viability and fertility are persons who were enrolled and who have nodulectomies performed 18 months after treatment. The study population for secondary efficacy outcomes related to microfilariae in the skin are participants who were enrolled in the study who have follow-up microfilaria testing by skin snip examination at time points (12, 18 months) as indicated in the diagram on page 26 of the protocol. The study population for the early (7 day) safety analysis are participants who receive the study drugs who have safety assessments during the 7 days after dosing. A separate safety analysis will consider data from the follow-up examinations conducted 3 months after dosing.

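### Student's t-test is the wrong test for individual yes/no adverse events in three arms: it is undefined with no events and unreliable when events are very few

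*Combined protocol and SAP*

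**What the plan says.** The safety part of section 8.2 names three methods.

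- For the overall comparison: "AE rates and severity will be compared across the three treatment groups using logistic regression analysis".
- In the same sentence, which is grammatically broken at the join, Student's "t -test will be used to assess differences for individual AEs".
- As a further look: "The data will also be examined using a generalized linear mixed model", described there as suited to non-normal outcomes.

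The main safety endpoint is also set there: "The primary safety analysis will focus on AEs with severity grade 3 or greater". All AEs and ocular AEs are secondary. Section 4 makes safety one of two primary objectives, worded as comparing both the rates and the types of severe AEs, but adds that "the safety study should be considered to be exploratory".

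No confidence interval is planned for any AE comparison. No expected AE rate and no significance level for safety tests are given.

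**The concern.** A participant either has a given AE or does not. Student's t-test compares two means under a common variance and takes its standard error from the observed variance. With 0/1 data and no events in either arm, that variance is zero and the test statistic is 0/0. With events in one arm only, the empty arm adds nothing to the standard error, as if its rate were known to be exactly zero. The test also handles two groups, while the plan has three and does not say which pairs are meant. Elsewhere section 8.2 treats binary outcomes (worm fertility, zero skin Mf) with binomial models, so this sentence is out of line with the plan's own practice.

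The stake is how much harm remains compatible with the data. Ivermectin pretreatment and the ocular exclusions in section 4.2 are meant to make severe and ocular events rare, so zero or one event per arm for a given term is an expected result. Section 4 says the data should help to justify or rule out a larger safety study. A method that returns nothing, or understates the upper limit, serves that decision poorly.

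**Working it through.** **Inputs.** Section 8.1 gives at least 61 per arm (51 × 1.2 = 61.2). Section 4.1 gives up to 300 participants, and section 4.4 an even split within strata, so at most about 300/3 = 100 per arm. The documents state no safety figure to reproduce. Assumed here: each AE is counted once per participant; tests are two-sided at 0.05 (section 8.1 states this level for efficacy only); true AE rates range from 0% to 15%.

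**Step 1: no events in either arm.** Both sample variances are 0, so the standard error is 0, the test is undefined and the interval has zero width. By contrast, the Wilson upper limit for 0/61 is 1.96²/(61 + 1.96²) = 3.84/64.84 = 5.9%, which gives a Newcombe interval for the difference of −5.9% to +5.9%. The chance of 0 vs 0 is (1 − p)^(2n) when both true rates are p:

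| True rate, both arms | 61 per arm | 100 per arm |
|---|---|---|
| 0.1% | 88.5% | 81.9% |
| 0.5% | 54.3% | 36.7% |
| 1% | 29.3% | 13.4% |
| 2% | 8.5% | 1.8% |

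**Step 2: 0 vs 1 event, 61 per arm.** The difference is d = 1/61 = 1.64%. The sample variance in the arm with the event is (61/60)(1/61)(60/61) = 1/61; in the other arm it is 0. So SE = √[(1/61 + 0)/61] = 1/61 = 1.64%. With t(0.975; 120 df) = 1.980, the interval is 1.64% ± 1.980 × 1.64%, or −1.6% to 4.9%.

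The Miettinen-Nurminen limits are the values δ at which |d − δ| / √{[p̃₁(1 − p̃₁) + p̃₂(1 − p̃₂)]/n × 2n/(2n − 1)} = 1.96, where p̃₁ and p̃₂ are the maximum-likelihood rates constrained to differ by δ. The upper limit is about 8.8%. At 100 per arm the two upper limits are 3.0% and 5.5%.

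**Step 3: how fast the problem fades.** Interval widths at 61 per arm, in percentage points:

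| Events | t | Miettinen-Nurminen |
|---|---|---|
| 1 vs 5 | 15.5 | 18.0 |
| 5 vs 12 | 24.7 | 25.3 |
| 10 vs 20 | 30.6 | 30.2 |

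**Step 4: coverage of the nominal 95% t interval.** Coverage is the sum, over all event counts in the two arms, of the product of the two binomial probabilities wherever the interval contains the true difference.

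| Assumed true rates | 61 per arm | 100 per arm |
|---|---|---|
| 0% vs 2% | 70.7% | 86.6% |
| 0.5% vs 2% | 77.3% | 86.4% |
| 1% vs 3% | 83.8% | 93.6% |
| 5% vs 15% | 94.6% | 95.0% |

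The first entry can be checked by hand. With rates 0% and 2%, the result is 0 vs 0 with probability 0.98^61 = 29.2%, and the zero-width interval then misses the true 2%, so coverage cannot exceed 70.8%. At 0.5% vs 2% and 61 per arm, the true excess lies above the upper limit in 22.6% of trials and below the lower limit in 0.1%.

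**Step 5: false positives.** With equal true rates at 61 per arm, the t-test rejects in 0.4% of trials at a rate of 1%, 2.0% at 2%, 4.6% at 5% and 5.1% at 10%.

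**The case against.** The strongest reply is about reach. The t-test applies only to individual AEs. The main comparison of AE rates and severity uses logistic regression, a mixed model is added, and safety is declared exploratory. The DSMB's case review and pausing procedures in section 7.7 do not rest on a t-test. All of this stands, and it limits the weight of the point. It does not make the t-test suitable. Nor does logistic regression fill the gap: by ordinary maximum likelihood, the estimate for an arm with no events runs off to minus infinity on the log-odds scale, and section 8.2 names no remedy.

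Two stronger readings are tempting and are not supported.

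- A reader might infer that the trial will report safety intervals that are far too narrow. The plan promises no t-based interval, so that consequence arises only if one is derived from the test. Even then the shortfall is large only with a handful of events. Common reactions such as pruritus or headache may occur at rates where the t interval performs acceptably.
- A reader might infer that the t-test will produce spurious safety signals, because 0 vs 4 events at 61 per arm gives p = 0.042 against 0.119 by Fisher's exact test. Step 5 shows no material inflation, and the Miettinen-Nurminen interval for the same data, 0.4% to 15.7%, also excludes zero. The contrast mainly reflects the conservatism of Fisher's test and is not evidence against the t-test.

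**Conclusion.** The plan names the wrong test for individual AEs, and this should be corrected. The failure at 0 vs 0 events needs no assumption beyond yes/no counting per participant. The understated upper limit (4.9% against about 8.8% at 0 vs 1, 61 per arm) applies only if an interval is taken from the test. Coverage between 71% and 95% depends on assumed true rates and is not a property of this trial. The defect is confined to rare events in comparisons of individual AEs, within a safety study declared exploratory. It gives no reason to doubt the efficacy analysis, the sample size or the DSMB arrangements.

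**What to change.** In section 8.2, replace the t-test clause with text to this effect:

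*For each AE term, and for grade 3 or higher AEs when an arm has zero or few events, the number of participants with the event will be reported by arm, with the risk difference of IDA x1 and of IDA x3 vs IVM/ALB and its 95% confidence interval by the Miettinen-Nurminen (score) or an exact method. If a p-value is given, it will come from the test that matches the interval: a score test with the score interval, or an exact test with the exact interval.*

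One interval method should be named in advance. The matching rule matters because a score interval paired with a Fisher p-value can disagree, as at 0 vs 4 above. The change should be made before treatment assignments are unmasked for the 3-month safety comparison (section 4.5). It costs a short rewrite of a sentence that needs repair anyway and changes neither data collection nor sample size. The downside is wider intervals for rare events.

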8.3 Interim and Final Reports

An interim clinical trial report will be prepared and submitted to the Ghana FDA, IRB/ECs, and other relevant regulatory agencies after the 3-month safety assessments are complete. A final

report will be prepared and submitted to the same groups not later than 90 days after the completion of the trial (after the last patient, last visit for nodulectomy). Investigators will prepare these reports in accordance with the comprehensive formal report conforming to the *ICH E3 Guideline for the Structure and Content of Clinical Study Reports* as per sub-section 3.6.4.1 of the FDA's Guidelines for Authorization of Clinical Trials.

The biostatistician will generate tables, figures and listing during data analysis (after final follow-ups) during which time, they will review the data for missing, unused and spurious data. Study staff will report any major changes to the statistical analysis plan to the IRB at UHAS and the Ghana Health Service and to the DSMB. In addition, any major changes will be reported to the FDA prior to datalock.

9 DATA HANDLING

Data will be collected using a tablet-based system, pre-loaded with study templates. Study staff will be trained in the use of the instruments and data will be uploaded as entries are completed.

Washington University in St. Louis will serve as the data coordinator for the study. The data will be owned by study investigators at UHAS School of Public Health Research Centre. The data will be compiled, validated and cleaned at UHAS School of Public Health Research Centre. Data will be accessible to Washington University in St. Louis for further validation checks and data cleaning. After data have been cleaned and finalized, the database will be locked, and the final dataset will be accessible to investigators at the University of Health and Allied Sciences School of Public Health Research Centre. Data analysis will be a collaborative effort between University of Health and Allied Sciences School of Public Health Research Centre and investigators at Case Western Reserve University and Washington University in St. Louis.

9.1 Types of Data Collected

Enrollment Data

- Participant identifier
- Informed consent date
- Demographic information (date of birth, gender)
- Pregnancy/breastfeeding status
- Medical history
- Presence of onchocercal nodules
- History of prior MDA treatment
- Physical exam
- Skin exam (including photographs of skin lesions)
- Ocular exam (including retinal and ocular coherence tomography photographs)

Laboratory Results

- Skin snip (including MF count)
- Nodule histology results (number of live/dead female and male worms, etc.)

Participant Monitoring and Follow-up

- Physical exam
- Skin exam (including photographs of skin lesions)
- Ocular exam (including retinal and ocular coherence tomography photographs)

Adverse Event Evaluation

- Adverse event assessment
- Treatment assignment
- Concomitant medication
- Ae description
- Start and stop date
- Outcome
- SAE evaluation and causality to MDA (definite, probable, possible, or unrelated)

9.2 Study Records Retention

Study documents will be retained for a minimum of seven (7) years after the study has been closed. These documents will be retained for a longer period if required by local regulations. No record will be destroyed without the written consent of DOLF and UHAS investigators.

The principle investigator at the study site will maintain appropriate medical and research records for this trial, in compliance with ICH E6, Section 4.9, regulatory and institutional requirements for the protection of confidentiality of participants. The investigator will permit authorized representatives of the sponsor and regulatory agencies to examine (and when required by applicable law, copy) clinical records for the purposes of clinical site monitoring, quality assurance reviews, audits, and evaluation of the study safety and progress.

9.3 Participant Key/Participant List

The participant key linking the list of all study participants with their unique identifier will only be available to the Ghanaian PI and to study personnel who have been delegated authority to handle the participant key. The participant key may be paper or electronic. The participant key will not be shared with investigators outside of Ghana.

9.4 Source Documents

This study may use paper and/or electronic source records. An electronic data capture system (EDC) will be employed to record data either directly into electronic forms or entered into the EDC from paper forms. Paper data collection forms derived from the electronic case report forms (eCRFs) will be available to study staff as a backup. The selected EDC vendor will be 21 CFR 11 compliant including audit trails, time stamps, and encryption with secure password protected access.

Source documents will be stored for the duration of the study plus 7 years. The electronic database (study data) will be stored for 7 years by the Principle Investigators' institution. Source documents may be stored longer if required by regulatory requirements.

10 FUTURE USE OF STORED SPECIMENS

Samples collected in this study may be used for research related to onchocerciasis (diagnosis, parasite variability, treatment, or the pathogenesis of adverse events). Any other uses will require the prior approval of either the Washington University or University Hospitals Cleveland Medical Center (UHCMC) IRB, and the GHS-Ethical Review Committee and the UHAS Research Ethics Committee. Any use of samples outside of Ghana will require removal of any identifying information apart from study identification numbers. Subjects may still participate in this study even if they do not consent to use of their samples for future scientific studies. If the subject checks “no,” (in the informed consent document), then their samples will be stripped of its identification number in the database after the completion of this study and the samples will not be used.

11 ETHICAL ISSUES

11.1 Informed Consent Process

Project investigators will consent eligible individuals in their own villages prior to the 6-month follow up of the Part I study. The Site PI or a co-investigator will inform the subjects of all aspects of the study covering all elements of informed consent. The study details will be explained in the local language Konkomba or Twi or in another language understood by the participant.

Project investigators will consent eligible individuals in their communities prior to enrollment into the IDA study. The Site PI or a co-investigator will inform the subjects of all aspects of the study covering all elements of informed consent. The study details will be read and explained in the local language (Konkomba or Twi) to the participant.

An informed consent document that is specific to the study will be available in English and the local language (Appendix F). The investigator must use an IRB/ERC approved informed consent document. Adequate time will then be allowed for the subjects to ask questions and make individual voluntary decisions. The form will be signed by the participant (or thumbprint) witnessed by an impartial community member and signed by an investigator ([name], [name], [name], [name]). A copy of the information document and the consent will be given to the subject. A second copy of the consent will be stored in the Investigator’s file. Only individuals who have signed the consent form and meet eligibility criteria will be enrolled in the study.

After the 18 month follow-up and nodulectomies, analysis will be done to determine the effectiveness of the drug therapies. All participants in less effective treatment arms will be offered the more effective treatment at no cost to the participant.

